^b Day 1 (AZD7442 IV administration): Perform vital signs (including pulse oximetry) within 15 minutes prior to the start of infusion, every 15 minutes (± 5 minutes) during the infusion, and 15 minutes (± 5 minutes) after end of infusion.
 Days 183 and 365 (AZD7442 IM administration): Perform vital signs (including pulse oximetry) predose (within 15 minutes prior to first injection) and postdose (15 minutes [± 5 minutes] after both injections are complete).

- ^c FSH will be analyzed at screening to confirm postmenopausal status only in women < 50 years of age who have been amenorrhoeic for ≥ 12 months. Until FSH is documented to be within menopausal range, the participant is to be considered of childbearing potential. For women aged ≥ 50 years, postmenopausal is defined as having a history of ≥ 12 months' amenorrhea prior to Day 1, without an alternative cause, following cessation of exogenous sex-hormonal treatment.
- ^d This test is not performed as part of the clinical study but must be available prior to enrollment.
- ^e If a documented (negative) SARS-CoV-2 RT-PCR test is not available at screening, a SARS-CoV-2 rapid antigen test will be performed. Either test must be negative before dosing (see inclusion criteria in Section 5.1).
- ^f Baseline sample, not a screening sample; results not needed prior to randomization.
- ^g If the urine pregnancy test is positive or indeterminate, a quantitative serum β -hCG will be performed by the central laboratory for confirmation.
- ^h On Day 1, a negative urine pregnancy test is required before the participant receives IMP.
- ⁱ For all participants, the PK and NLF samples will be collected postdose within 30 minutes after the end of infusion on Day 1.
- ^j For a subset of 20 participants, PK and NLF samples will be collected at 24 to 72 hours after the Day 1 AZD7442 dose.
- ^k For a subset of 20 participants, PK and NLF samples will be collected at Day 11 (± 3 days).
- ^l When test supplies are available, sampling should be performed.
- ^m Includes monitoring participants for at least one hour postdose, checking injection sites, and monitoring for hypersensitivity (including anaphylaxis), and infusion-related reactions (applicable for Day 1 IV administration). On Day 1, the minimum of one hour postdose monitoring will start at the end of the IV infusion. See Section 8.2.5 for required safety monitoring.

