6.1 Study Intervention(s) Administered

6.1.1 Investigational Medicinal Products

The IMP to be administered in this study is described in [Table 6](#).

Table 6 Investigational Medicinal Products

Intervention name	AZD7442 (tixagevimab [AZD8895] + cilgavimab [AZD1061])
Type	Biologic
Dose formulation	Liquid Product AZD7442 will be supplied as separate vials of tixagevimab (AZD8895) and cilgavimab (AZD1061) as 150 mg colorless to slightly yellow, clear to opalescent solutions for injection. The solutions contain 100 mg/mL of active ingredient (tixagevimab [AZD8895] or cilgavimab [AZD1061]) in 20 mM L-histidine/L-histidine hydrochloride, 240 mM sucrose, and 0.04% (w/v) polysorbate 80, at pH 6.0. The label-claim volume is 1.5 mL.
Unit dose strength(s)	150 mg (nominal) tixagevimab (AZD8895) and 150 mg (nominal) cilgavimab (AZD1061) per vial.

Table 6 Investigational Medicinal Products

Dosage level(s) and route of administration	
AZD7442 doses (combined doses of tixagevimab [AZD8895] and cilgavimab [AZD1061]) to be administered:
 
Arm A (AZD7442 600 mg IM on Day 1 then 300 mg IM Q3M for 12 months)
 
 • Day 1 600 mg AZD7442 administered sequentially as a 3 mL IM injection containing 300 mg tixagevimab (AZD8895) and a 3 mL IM injection containing 300 mg cilgavimab (AZD1061), one injection in each gluteal region. • Days 92, 183, 274, 365 300 mg AZD7442 administered sequentially as a 1.5 mL IM injection containing 150 mg tixagevimab (AZD8895) and a 1.5 mL IM injection containing 150 mg cilgavimab (AZD1061), one injection in each gluteal region. 
Arm B (AZD7442 1200 mg IV on Day 1 then 600 mg IM Q6M for 12 months)
 
 • Day 1 1200 mg AZD7442 (600 mg tixagevimab [AZD8895] and 600 mg cilgavimab [AZD1061]) administered by IV infusion. • Days 183, 365 600 mg AZD7442 administered sequentially as a 3 mL IM injection containing 300 mg tixagevimab (AZD8895) and a 3 mL IM injection containing 300 mg cilgavimab (AZD1061), one injection in each gluteal region.
Use	Experimental
IMP or NIMP	IMP
Sourcing	AZD7442 (tixagevimab [AZD8895] + cilgavimab [AZD1061]): AstraZeneca.
Packaging and labeling	IMP will be provided in a glass vial. Each glass vial will be labeled as required per country requirement.

IM, intramuscular; IMP, investigational medicinal product; IV, intravenous; Q3M, every 3 months; Q6M, every 6 months; w/v, weight per volume.

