6.2.1 Dose Preparation and Administration Instructions

Each vial selected for dose preparation should be inspected. If there are any defects noted with the IMP, the Investigator and site monitor should be notified immediately.

AZD7442 IMP is comprised of 2 separate DPs, tixagevimab (AZD8895) and cilgavimab (AZD1061). Tixagevimab (AZD8895) and cilgavimab (AZD1061) DPs are each supplied as sterile clear to opalescent, colorless to slightly yellow solutions, with a label-claim of 150 mg at 100 mg/mL per vial.

The dose of tixagevimab (AZD8895) and cilgavimab (AZD1061) for administration must be prepared using aseptic technique. Total time from needle puncture of the vial to the start of administration must not exceed:

- 24 hours at 2 °C to 8 °C (36 °F to 46 °F)
- 4 hours at room temperature.

If the final product is stored at both refrigerated and ambient temperatures, the total time must not exceed 24 hours, otherwise a new dose must be prepared from new vials. Each tixagevimab (AZD8895) and cilgavimab (AZD1061) vial must be used only once to prepare a single dose. AZD7442 (tixagevimab [AZD8895] and cilgavimab [AZD1061]) does not contain preservatives, and any unused portion must be discarded.

6.2.1.1 AZD7442 IV 1200 mg (600 mg Tixagevimab [AZD8895] and 600 mg Cilgavimab [AZD1061]) Dose Preparation and Administration Instructions (Arm B; Day 1 Only)

Use a single IV bag with diluent of 0.9% (w/v) sodium chloride or 5% dextrose to co-administer tixagevimab (AZD8895) and cilgavimab (AZD1061) infusion. The admixture can be prepared using IV bag volumes ranging between 50 mL and 250 mL and the IV bag material of construction may consist of polyolefin, polyvinylchloride, or polyethylene.

To prepare the IV bag, accurately withdraw 6 mL of tixagevimab (AZD8895) and 6 mL of cilgavimab (AZD1061) and transfer both to the same IV bag. Mix the contents of the bag until visually uniform.

Administer the entire contents of the IV bag using IV administration sets containing low protein binding 0.2 micrometre or 0.22 micrometre filters made of polyethersulfone. The target infusion rate is 20 mg/minute.

The IV line and catheter must be flushed according to local practices to ensure the full dose is administered.

Monitoring for safety, including infusion-related reactions and hypersensitivity reactions is described in Section 8.2.5.

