3.3.2 Visit Window

A windowing convention will be used to determine the analysis value for a given study visit for visit-based assessments, which are as follows:

- Serum sample for SARS-CoV-2 serology (anti-nucleocapsid testing)
- Serum sample for AZD7442 PK assessments
- Serum sample for AZD7442 ADA
- Serum sample for SARS-CoV-2 nAbs levels (pharmacodynamics [PD])
- Serum sample exploratory biomarkers
- Nasal lining fluid sample for AZD7442 PK assessments
- Clinical chemistry, hematology, coagulation, and urinalysis
- Vital signs
- Electrocardiogram (ECG)
- Illness visits for COVID-19 symptom assessment, vital signs, immunogenicity, PD, PK, coagulation, serum sample for exploratory assessments

The window for the visits following baseline will be constructed in such a way that the upper limit of the interval falls halfway between the two visits (the lower limit of the first post-baseline visit will be Day 2). If an odd number of days exists between two consecutive visits, then the upper limit will be taken as the midpoint value minus 1 day.

One or more results for a particular variable may be obtained in the same visit window. In such an event, the result with the date closest to the expected visit date will be used in the analysis. In the event that two observations are equidistant from the expected visit date, the later observation will be used in the analysis.

The visit windows are defined in the following tables.

Table 3: Analysis windows for serum sample for SARS-CoV-2 serology, ADA and SARS-CoV-2 nAbs levels

Arm A

Visit	Day Relative to First Dose	Visit Window (Study Day)
Day 1	≤ 1	≤ 1
Day 29	29	2 – 60
Day 92	92	61 - 106
Day 121	121	107 - 152
Day 183	183	153 - 197
Day 212	212	198 - 242
Day 274	274	243 - 319
Day 365	365	320 - 410
Day 456	456	≥411 [for serology and SARS-CoV-2 nAbs] 411 – 592 [for ADA assessment]
Day 729 (Follow-up)	729	≥593 [for ADA assessment]

Arm B

Visit	Day Relative to First Dose	Visit Window (Study Day)
Day 1	≤ 1	≤ 1
Day 29	29	2 – 60
Day 92	92	61 - 137
Day 183	183	138 - 197
Day 212	212	198 - 242
Day 274	274	243 - 319
Day 365	365	320 - 410
Day 456	456	≥411 [for serology and SARS-CoV-2 nAbs] 411 – 592 [for ADA assessment]
Day 729 (Follow-up)	729	≥593 [for ADA assessment]

Table 4: Analysis windows for serum sample for AZD7442 PK assessment, NLF sample for mucosal response

Arm A

Visit	Day Relative to First Dose	Visit Window (Study Day)
Day 3	3	2 – 6 [subset of 20 participants, PK and NLF assessment]

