Day 1, During Dose, 30 mins	1	>22 minutes 30 seconds post 1 st IMP dose time - ≤ 37 minutes 30 seconds minutes post 1 st IMP dose time
Day 1, During Dose, 45 mins	1	>37 minutes 30 seconds post 1 st IMP dose time - ≤ 52 minutes 30 seconds post 1 st IMP dose time
Day 1, During Dose, 60 mins	1	> 52 minutes 30 seconds post 1 st IMP dose time - ≤ 67 minutes 30 seconds post 1 st IMP dose time
Day 1, Post-dose	1	1, >67 minutes 30 seconds post 1 st IMP dose time
Day 29	29	2 - 60
Day 92	92	61 - 137
Day 183, Pre-dose	183	138 – 197, ≤ 2 nd IMP dose time
Day 183, Post-dose	183	138 – 197, > 2 nd IMP dose time

Visit	Day Relative to First Dose	Visit Window (Study Day)
Day 212	212	198 - 242
Day 274	274	243 - 319
Day 365, Pre-dose	365	320 – 410, \leq 3 rd IMP dose time
Day 365, Post-dose	365	320 – 410, $>$ 3 rd IMP dose time
Day 456	456	411 - 592
Day 729 (Follow-up)	729	\geq 593

Table 8: Analysis windows for ECG

Arm A

Visit	Day Relative to First Dose	Visit Window (Study Day)
Screening	<1	<1
Day 1	1	1
Day 92	92	2 - 137
Day 183	183	138 - 228
Day 274	274	229 - 319
Day 365	365	320 - 410
Day 456	456	\geq 411

Arm B

Visit	Day Relative to First Dose	Visit Window (Study Day)
Screening	<1	<1
Day 1	1	1
Day 183	183	2 - 273
Day 365	365	274 - 410
Day 456	456	\geq 411

Table 9: Analysis windows for immunogenicity, PD, PK, coagulation, serum sample for exploratory assessments (Illness visit schedule)

Visit	Day Relative to Illness	Visit Window (Study Day)
Illness Day 1	≤ 1	≤ 1
Illness Day 14	14	≥ 2

Table 10: Analysis windows for COVID-19 symptom assessment, SARS-CoV-2 RT-PCR sequencing NP swab, and vital signs (for Confirmed Illness visit schedule)

Visit	Day Relative to Illness	Visit Window (Study Day)
Illness Day 1	≤ 1	≤ 1

Visit	Day Relative to Illness	Visit Window (Study Day)
Illness Day 5	5	2- 5
Illness Day 7	7	6 - 10
Illness Day 14	14	≥11 (for Vital signs) 11 – 20 (for Covid-19 symptoms)
Illness Day 28	28	21 – 58 (for Covid-19 symptoms)
Illness Day 90	90	≥59 (for Covid-19 symptoms)

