3.3.3 Handling of Unscheduled Visits

Unscheduled, retest (same visit number assigned), and early discontinuation measurements will contribute to the summaries. Visits for visit-based data will follow a windowing convention as described in Section 3.3.2. If there are multiple observations collected at the same date and time, unscheduled visit record will be considered last.

Listings will include scheduled, unscheduled, retest and early discontinuation data.

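### The Arm B Day 1 'Post-dose' vital-sign window in SAP Table 7 runs from the start of dosing, so after an infusion of 52.5 minutes or less the scheduled post-dose reading is labelled 'During Dose'

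*SAP*

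**What the plan says.** **Protocol.** On Day 1, Arm B receives "1200 mg AZD7442 (600 mg tixagevimab [AZD8895] and 600 mg cilgavimab [AZD1061]) administered by IV infusion" (Table 6). Section 6.2.1.1 adds: "The target infusion rate is 20 mg/minute". It gives no tolerance and no minimum duration. Footnote b of the Arm B schedule (Table 2) requires vital signs "every 15 minutes (± 5 minutes) during the infusion" and again "and 15 minutes (± 5 minutes) after end of infusion".

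**SAP.** Section 3.3.2 assigns readings to time points by window. For Arm B Day 1, Table 7 has four 'During Dose' slots (15, 30, 45 and 60 mins) with upper limits of 22.5, 37.5, 52.5 and 67.5 minutes from the first IMP dose time, each limit included. The 'Post-dose' row is "1, >67 minutes 30 seconds post 1 st IMP dose time". No row refers to the end of infusion. Dose time is not defined in words as the start of infusion, but the first 'During Dose' slot opens immediately after it, so no other reading makes sense.

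Where several results fall in one window, Section 3.3.2 takes the one dated closest to the expected visit date. If they are equidistant, "the later observation will be used in the analysis". Section 3.3.3 adds: "Unscheduled, retest (same visit number assigned), and early discontinuation measurements will contribute to the summaries". Section 4.3.4.2 then summarises observed values and changes from baseline by visit.

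**The concern.** The two documents time the same reading from different points, the protocol from the end of infusion and the SAP from its start. They agree only when the infusion lasts about as long as planned.

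After a short infusion, a post-dose reading taken on schedule falls before 67.5 minutes and gets a 'During Dose' label although drug has stopped. The protocol schedules no later Day 1 vital signs, so the 'Post-dose' row loses that participant unless an extra reading happens to have been taken.

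The selection rule can add to this. Take a 56-minute infusion with the 60-minute reading taken 5 minutes early (55 minutes) and the post-dose reading taken 10 minutes after the end (66 minutes). Both fall in the 60-minute 'During Dose' slot and share a date, so the later, off-drug value replaces the on-drug one.

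This is the trial's only intravenous dose, and infusion-related reactions are an AESI. The on-infusion and post-infusion rows should therefore mean what they say.

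**Working it through.** **Inputs.** Dose 1200 mg (Protocol Table 6); target rate 20 mg/minute (Protocol 6.2.1.1); post-dose reading 15 ± 5 minutes after the end of infusion (Protocol Table 2, footnote b); window limits from SAP Table 7.

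**Reproducing the SAP cut.** Planned duration = 1200 / 20 = 60 minutes. Nominal post-dose reading = 60 + 15 = 75 minutes from the start. The midpoint of 60 and 75 is 67.5, the SAP's figure. The other cuts are the midpoints of 15/30, 30/45 and 45/60. The table is therefore built on a 60-minute infusion.

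**Short infusions.** For an infusion of T minutes the post-dose reading falls between T + 10 and T + 20 minutes from the start, nominally at T + 15. It is labelled 'Post-dose' only if that time exceeds 67.5. It is mislabelled:

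- at nominal timing when T + 15 ≤ 67.5, so T ≤ 52.5 (rate ≥ 1200 / 52.5 = 22.9 mg/minute; 22.9 / 20 = 1.14);
- at the earliest allowed time when T + 10 ≤ 67.5, so T ≤ 57.5 (1200 / 57.5 = 20.9 mg/minute);
- at every allowed time when T + 20 ≤ 67.5, so T ≤ 47.5 (1200 / 47.5 = 25.3 mg/minute).

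| T (min) | Rate (mg/min) | Label at T + 10 | Label at T + 15 | Label at T + 20 |
|---|---|---|---|---|
| 45 | 26.7 | During, 60 mins | During, 60 mins | During, 60 mins |
| 47.5 | 25.3 | During, 60 mins | During, 60 mins | During, 60 mins |
| 50 | 24.0 | During, 60 mins | During, 60 mins | Post-dose |
| 52.5 | 22.9 | During, 60 mins | During, 60 mins | Post-dose |
| 55 | 21.8 | During, 60 mins | Post-dose | Post-dose |
| 57.5 | 20.9 | During, 60 mins | Post-dose | Post-dose |
| 60 | 20.0 | Post-dose | Post-dose | Post-dose |

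The share of the allowed 10-minute window that is labelled 'During Dose' is (57.5 − T) / 10, limited to 0–1. That is 75% at T = 50, 50% at T = 52.5 and 25% at T = 55. These are shares of the window, not probabilities. At nominal timing, infusions of more than 37.5 and up to 52.5 minutes put the value in the 60-minute slot. Shorter ones put it in an earlier slot; at T = 30 the reading at 45 minutes goes to the 45-minute slot.

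**Long infusions.** With readings every 15 minutes, one during-infusion reading falls after 67.5 minutes at T = 75 (1200 / 75 = 16.0 mg/minute) and two at T = 90 (75 and 90 minutes). The true post-dose readings are then at 90 and 105 minutes. They are later on the same date, so the selection rule normally keeps them. What remains is that late during-infusion values drop out of the summary, or stand as 'Post-dose' if the true reading is missing.

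**Range without error.** If ± 5 minutes applies to a fixed clock from infusion start, no scheduled reading is mislabelled for T over 57.5 and under 70. If it applies to the gap between readings, the range is over 57.5 up to 67.5. For example, readings at 17, 34, 51 and 68 minutes are possible in a 69-minute infusion.

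**The case against.** The strongest reply is that Table 7 is correct for the infusion the protocol specifies. At 60 minutes every compliant post-dose reading (70 to 80 minutes) is labelled correctly, and the cuts follow the SAP's own halfway convention. At nominal timing the error needs an average rate at least 14% above target, and no document reports a short infusion. The protocol also requires the whole bag to be given and the line flushed, which if anything points away from short infusions. No hypothesis is tested, the listings are complete, counts of any abnormal value ignore the label, and infusion-related reactions are reported as AESIs.

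All of that stands as a limit on importance. It does not make the rule right, because 20 mg/minute is only a target and no other SAP rule recovers a short-infusion reading: the selection rule works by date.

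There are also fair points against the remedy. It depends on an end time that the protocol does not clearly require in the eCRF; Section 6.4 mentions the dose date, with time where applicable. It treats scheduled and unscheduled readings differently. It also still labels a scheduled reading taken within 7.5 minutes after the end as 'During Dose'. That last feature is deliberate, since a during-infusion reading due at the end may be taken up to 5 minutes late. The current table does the same for a 60-minute infusion.

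**Conclusion.** The concern holds, as a minor one. Table 7 gives the wrong label to a correctly timed post-dose reading for infusions of 52.5 minutes or less at nominal timing, 57.5 minutes or less if the reading is 5 minutes early, and at any allowed time for 47.5 minutes or less. The long side matters little.

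The effect is confined to the descriptive Arm B Day 1 rows of the vital-sign summary, and no study conclusion would change. The result assumes that dose time means the start of infusion. The number of participants affected is unknown from the documents and may be zero. A tabulation of Day 1 infusion durations would settle it.

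**What to change.** In SAP Table 7, Arm B, Day 1:

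- For scheduled readings, define 'Post-dose' as more than 7 minutes 30 seconds after the recorded end of infusion.
- For unscheduled readings, define it as any time after the end of infusion.
- Keep earlier readings after infusion start in the existing 15-minute 'During Dose' slots, and add a '> 60 mins' slot for those after 67.5 minutes.
- If the end time is missing, keep the present 67.5-minute cut.

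The 7.5-minute cut works for every duration. A scheduled during-infusion reading falls no later than T + 5 and a scheduled post-dose reading no earlier than T + 10. At T = 60 the cut is 60 + 7.5 = 67.5 minutes, so no scheduled label changes. An unscheduled reading at 65 minutes would move from 'During Dose, 60 mins' to 'Post-dose'.

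The cost is one table edit and its derivation, provided the infusion end time is in the analysis database. Sites must know it, because three Day 1 procedures run from it: the post-dose vital signs, the one-hour monitoring, and the samples for which Protocol Table 2 states "the PK and NLF samples will be collected postdose within 30 minutes after the end of infusion on Day 1". That does not prove it was entered, so the sponsor should confirm this first.

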- ^d IL-D1b assessments should only be performed if either the SARS-CoV-2 rapid antigen or RT-PCR local test result is positive. If the rapid antigen local test result is negative and the RT-PCR local test result is subsequently determined as positive (ie, rapid antigen was false negative), then IL-D1b assessments should be performed as soon as possible (but no later than 2 days) after the positive RT-PCR local test result is available. If the rapid antigen local test result is positive and the RT-PCR local test result is subsequently determined as negative (ie, rapid antigen was false positive), the participant will be instructed to discontinue Illness Visits.
- ^e To be collected when operationally viable.
- ^f When test supplies are available, sampling should be performed.
- ^g Symptom assessment to continue every 3 months until symptoms have resolved or end of study occurs. A separate visit is not required, the assessment should be performed at the next scheduled visits per [Table 1](#) for Arm A and [Table 2](#) for Arm B.
- ^h Targeted physical examination per investigator discretion will include areas suggested by medical history, vulnerable conditions and reported clinical complaints during the study visit and may require height and weight.

Note: The Illness Visit schedule is to be performed in addition to the scheduled visits in the treatment period ([Table 1](#) for Arm A and [Table 2](#) for Arm B) and follow-up period ([Table 3](#) for Arm A and Arm B). Where visits coincide, all assessments from the scheduled visit and the Illness Visit should be performed.

ADA, antidrug antibody; AESI, adverse events of special interest; COVID-19, coronavirus disease 2019; D, day; ECG, electrocardiogram; IL, illness; NA, not applicable; nAb, neutralizing antibody; NLF, nasal lining fluid; PBMC, peripheral blood mononuclear cell; PK, pharmacokinetics; PD, pharmacodynamics; RT-PCR, reverse transcriptase polymerase chain reaction; SAE, serious adverse event; SARS-CoV-2, severe acute respiratory syndrome-coronavirus-2.

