3.3.1 General Study Level Definitions

Reference start date and study day

Study Day will be calculated from the reference start date and will be used to show start/stop day of assessments and events. Reference start date is defined as the first day of the dose of IMP i.e., Day 1.

Study Day will be computed as follows:

- *Study Day = (Date of assessment/event – Date of first dose of IMP) + 1 if the date of the assessment/event is on or after the date of the first dose of IMP.*

- *Study Day = (Date of assessment/event – Date of first dose of IMP) if the date of the assessment/event is prior to the date of the first dose of IMP.*

In general, when the assessment/event date is partial or missing, Study Day and any corresponding durations will be displayed as missing in the listings.

For illness visits, an illness study day will be calculated. The reference start date is defined as the day of first illness assessment, i.e., illness visit Day 1. This will be calculated separately for each illness episode.

Illness Study Day will be computed as follows:

- *Illness Study Day = (Date of assessment/event – Date of illness visit Day 1) + 1.*

Baseline

In general, baseline is defined as the last non-missing measurement taken prior to the first dose of IMP. If the last non-missing measurement is taken at same date and time of the dose of IMP, this measurement will be considered baseline, with the exception of adverse events (AEs) and non-IMP medications commencing on the date and time of the dose of IMP, these assessments will be considered post-baseline.

Illness Visit baseline is defined as the first non-missing measurement taken on Illness Visit Day 1. If there is no non-missing measurement available on Illness Visit Day 1, Illness Visit baseline is considered as missing. For instances, where Illness Visit Day 1 occurs on the same day as a main study Visit, and Illness Visit Day 1 measurements are missing, then the measurements from the main study Visit will be used as Illness Visit baseline. Otherwise, if there is still no available measurement for Illness Visit Day 1, Illness Visit baseline is considered as missing.

Change from baseline will be calculated as (*post-baseline visit – baseline visit*).

Change from baseline for Illness Visits will be calculated as:

- *Change from baseline at Illness Visit Day 1 = Test value at Illness Visit Day 1 – Baseline value*

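### SAP Table 9 labels late but permitted IL-D1b blood samples as Illness Day 14, so those episodes lose their Illness Day 1 value

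*SAP*

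**What the plan says.** **SAP Section 3.3.1** starts the illness clock at the first assessment of the episode: "The reference start date is defined as the day of first illness assessment, i.e., illness visit Day 1". Days are then counted by calendar date: "Illness Study Day = (Date of assessment/event – Date of illness visit Day 1) + 1". On baseline it says: "Illness Visit baseline is defined as the first non-missing measurement taken on Illness Visit Day 1", and "If there is no non-missing measurement available on Illness Visit Day 1, Illness Visit baseline is considered as missing". The only fallback is a main study visit held on that same day.

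**SAP Section 3.3.2, Table 9**, headed "Analysis windows for immunogenicity, PD, PK, coagulation, serum sample for exploratory assessments (Illness visit schedule", covers the illness-visit bloods. Illness Day 1 takes illness day 1 or earlier. The only other row reads "Illness Day 14 14 ≥ 2". Illness windows apply only to episodes with a laboratory-confirmed positive RT-PCR. If several results share a window, the one closest to the expected date is used, and a tie goes to the later one.

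**Protocol Section 1.3, Table 4** schedules none of these bloods at IL-D1a. Serum PK is drawn at IL-D1b only. ADA, nAb, coagulation and exploratory serum are drawn at IL-D1b and IL-D14 (± 2 days). Footnote d, repeated in Protocol Section 8.1.3, covers a negative antigen test followed by a positive local RT-PCR: "IL-D1b assessments should be performed as soon as possible (but no later than 2 days) after the positive RT-PCR local test result".

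**The concern.** The SAP window assumes that the acute-illness bloods are taken on the day the clock starts. The protocol allows them later in one defined situation, and a site that follows it exactly can produce an IL-D1b sample dated illness day 2 or beyond. Table 9 then treats that sample as a Day 14 sample.

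What is at stake is the acute-illness value for these episodes: the nAb titer, ADA result, coagulation results and exploratory serum at Illness Day 1, and the label on the single PK sample taken at breakthrough. The episodes concerned had a negative antigen test at presentation, so the Illness Day 1 summaries would lean towards antigen-positive episodes.

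**Working it through.** **1. Reproduce the plan's windows.** Section 3.3.2 starts the first post-baseline window at Day 2. Later upper limits are the midpoint between visits, less one day if an odd number of days lies between them.

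- Table 10, Days 5 and 7: one day between, midpoint 6, less 1 = 5.
- Days 7 and 14: six days between, midpoint 10.5, so 10.
- Days 14 and 28: thirteen days between, midpoint 21, less 1 = 20.
- Days 28 and 90: sixty-one days between, midpoint 59, less 1 = 58.

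All four match the printed limits. In Table 9 the first post-baseline visit is Illness Day 14, so its lower limit is 2, also as printed. Table 9 is therefore consistent with the SAP's own convention.

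**2. Where a late IL-D1b falls.** Illness study day = 1 + T + L. T is the number of days from IL-D1a to the RT-PCR result; the documents do not give it, so 0 to 3 is an assumed range. L is the permitted lag after the result, 0 to 2 days.

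| T (assumed) | Illness day of draw, L = 0, 1, 2 | Table 9 label |
|---|---|---|
| 0 | 1, 2, 3 | Day 1, Day 14, Day 14 |
| 1 | 2, 3, 4 | Day 14 |
| 2 | 3, 4, 5 | Day 14 |
| 3 | 4, 5, 6 | Day 14 |

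Only a draw on the IL-D1a date keeps the Illness Day 1 label.

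**3. Which sample represents Illness Day 14.** An on-schedule IL-D14 draw falls on days 12 to 16, at most 2 days from day 14. A late IL-D1b on day 2 is 14 − 2 = 12 days away; on day 6 it is 8 days away. The on-schedule sample always wins. The late IL-D1b is chosen only if the IL-D14 draw is missing or falls further from day 14:

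- IL-D1b on day 2: IL-D14 on day 27 or later (27 − 14 = 13 > 12).
- IL-D1b on day 3: day 26 or later (12 > 11).
- IL-D1b on day 6: day 23 or later (9 > 8).

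For nAb, ADA, coagulation and exploratory serum, the usual result is that the late sample appears under neither visit. PK has no scheduled IL-D14 draw to compete with it, so a late sample keeps the Illness Day 14 label.

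**4. Effect on baseline.** Read by date, a draw on day 2 or later is not taken on Illness Visit Day 1, so the Illness Visit baseline is missing unless a main study visit falls on that day. The planned analyses that could depend on it are:

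- Coagulation: SAP Section 4.3.3.2 plans change from baseline by illness visit. Under Section 3.3.1 the change at Illness Day 1 needs a Day 1 value and the later change needs the Illness Visit baseline, so both are lost.
- nAb: Section 4.2.2.4.2 plans titer and fold rise at illness visits. The Day 1 entry is lost, but fold rise divides by the pre-dose titer (Section 4.2.2.2.2), so its denominator stays.
- ADA: Sections 4.2.1.1 and 4.2.1.2 use study baseline and any post-baseline result. No illness change from baseline is specified.
- Serum PK: Section 4.2.2.4.1 specifies no summary by illness visit.

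**The case against.** The strongest reply is that Table 9 obeys the SAP's Day 2 rule, that nothing is tested (Section 3.3.4), and that little output depends on the label. Much of this stands, and it rules out several stronger readings.

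- *A reader might infer that Table 9 breaks the SAP's midpoint rule, which would put the cut at day 7.* It does not. The midpoint of 1 and 14 is 7.5, but Section 3.3.2 fixes the first post-baseline lower limit at Day 2.
- *A reader might infer that late IL-D1b samples are generally reported as Day 14 values.* For variables with an IL-D14 draw, this happens only when that draw is missing or very late.
- *A reader might infer that nAb and ADA change from baseline are lost.* Neither planned analysis uses the Illness Visit baseline.
- *A reader might infer that a breakthrough PK table would be wrong.* The SAP describes no such table. The nAb-PK correlation excludes illness samples, and PK at breakthrough appears only in a listing with variant data (Section 4.2.3.4.6).
- *A reader might infer that every antigen-negative, RT-PCR-positive episode is affected.* A same-day result with same-day bloods stays on day 1.

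The loss of baseline also depends on wording. If Illness Visit Day 1 means the nominal visit, which the protocol labels 1IL-D1, a late IL-D1b sample could still serve as baseline. The same sample would then be baseline and also be windowed to Illness Day 14, so that reading needs a clarifying sentence too.

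**Conclusion.** The mismatch is real. Applied exactly, the SAP removes the Illness Day 1 label from bloods that the protocol allows to be drawn after the IL-D1a date. The effect is limited to RT-PCR-confirmed episodes bled after that date; the documents give neither their frequency nor the RT-PCR turnaround.

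The firm consequences are a missing Illness Day 1 entry for nAb, ADA, coagulation and exploratory serum, and an Illness Day 14 label on late PK samples. On the date reading of baseline, the planned illness-visit coagulation change is also lost, unless a main study visit on the same day supplies the baseline. The fault is that the Day 2 convention does not fit IL-D1b timing; Table 9 was not derived wrongly. Severity is low to moderate, because only descriptive summaries are affected.

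**What to change.** 1. In Table 9, assign IL-D1b samples to Illness Day 1 by nominal visit, whatever the calendar date. Alternatively, as a stated exception to the Day 2 rule, use day 7 or earlier for Illness Day 1 and day 8 or later for Illness Day 14. That split covers a turnaround of up to 4 days with the full allowance (1 + 4 + 2 = 7) and does not touch scheduled IL-D14 draws on days 12 to 16. A turnaround of 5 days could reach day 8 and fall outside it, so the nominal-visit rule is safer.
2. In Section 3.3.1, state that for blood parameters the Illness Visit baseline is the IL-D1b sample.

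The cost is one table row and one sentence in the SAP. No new data are needed.
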